2.2.1 Study Population

2.2.1.1 Inclusion Criteria

Cohort Specific Inclusion Criteria

Phase 1b: Subjects that meet eligibility criteria for Phase 2 Cohorts 1 or 2 and all of the general eligibility criteria.

Phase 2 Cohort 1: Histologically or cytologically confirmed, immunotherapy naïve, metastatic or locally advanced non-small cell lung cancer not amenable to curative treatment. Subjects may be treatment naïve or could have received one prior platinum-based chemotherapy for non-small cell lung cancer for any indication (adjuvant, part of combined modality therapy or for metastatic disease) within the past 3 years. Subjects with no or unknown activating mutation (e.g., EGFR, ALK, ROS) are eligible for this study. Subjects with a documented activating mutation (e.g., EGFR, ALK, ROS) amenable to tyrosine kinase inhibitor therapy, must also have received the appropriate therapy and progressed.

Phase 2 Cohort 2: Subjects with histologically or cytologically confirmed unresectable or metastatic melanoma that had confirmed progressive disease during treatment with anti-PD-1/PD-L1 therapy. Subjects with BRAF wild type or unknown status must have received only anti-PD-1/PD-L1 therapy. Subjects with BRAF activating mutation could have also received a BRAF inhibitor and/or MEK inhibitor regimen prior to anti-PD-1/PD-L1 therapy.

Confirmed PD ([Section 5.2.1](#)) during treatment with anti-PD-1/PD-L1 therapy should be documented by 2 consecutive tumor assessments at least 4 weeks apart (the second scan may be used as the baseline scan for this study if it was performed within the 21 days prior Cycle 1 Day

1). Subjects should start study treatment no later than 8 weeks following the last dose of anti-PD-1/PD-L1 therapy (with no intervening therapy).

Subjects with ocular melanoma are excluded.

Phase 2 Cohort 3: Subjects with histologically or cytologically confirmed, metastatic or locally advanced NSCLC not amenable to curative treatment. Subjects must have disease progression on an immediately preceding PD-1/PD-L1 containing regimen. Subjects could have received no more than one platinum containing regimen, or if subjects have a documented activating mutation (e.g. EGFR, ALK, ROS) amenable to tyrosine kinase inhibitor therapy, must also have received the appropriate therapy and progressed before the PD-1/PD-L1 containing regimen. Based on response to previous PD-1/PD-L1 containing regimen, subjects will be enrolled in one of the following groups:

- Group A: Subjects with best response of progressive disease or with stable disease < 16 weeks
- Group B: Subjects with tumor response or with stable disease ≥ 16 weeks.

If possible, confirmed PD ([Section 5.2.1](#) during treatment with anti-PD-1/PD-L1 therapy should be documented by 2 consecutive tumor assessments at least 4 weeks apart (the second scan may be used as the baseline scan for this study if it was performed within the 21 days prior Cycle 1 Day 1). Subjects should start study treatment no later than 8 weeks following the last dose of anti-PD-1/PD-L1 containing regimen.

General Inclusion Criteria

1. Subjects willing and able to provide written informed consent for this study
2. Male or female ≥ 18 years old at time of consent
3. Measurable disease by Response Evaluation Criteria in Solid Tumors (RECIST) 1.1
4. Eastern Cooperative Oncology Group (ECOG) performance status of 0 or 1
5. Resolution of prior treatment-related toxicities to Grade 1, with the exception of alopecia, Grade 2 neuropathy and laboratory abnormalities (parameters below apply). If subject received major surgery or radiation therapy of > 30 Gy, they must have recovered from the toxicity and/or complications from the intervention
6. Adequate organ function within 14 days of first dose of investigational product:
 - a. White blood cell count (WBC) $\geq 1.5 \times 10^9/L$ in absence of growth factor support
 - b. Absolute neutrophil count (ANC) $\geq 1.0 \times 10^9/L$ in absence of growth factor support
 - c. Platelet count $\geq 100 \times 10^9/L$
 - d. Hemoglobin ≥ 8 g/dL
 - e. Serum creatinine ≤ 1.5 mg/dL AND creatinine clearance ≥ 60 mL/min (calculated [using the formula of local laboratory] or measured)
 - f. Aspartate aminotransferase (AST) and alanine aminotransferase (ALT) ≤ 2.5 x upper limit of normal (ULN)
 - g. Total bilirubin ≤ 1.5 x ULN, or direct bilirubin \leq ULN for subjects with total bilirubin levels > 1.5 x ULN
 - h. International Normalized Ratio (INR) or Prothrombin Time (PT) ≤ 1.5 x ULN unless subject is receiving anticoagulant therapy as long as PT or Partial Thromboplastin Time (PTT) is within therapeutic range of intended use of

anticoagulants

- i. Activated Partial Thromboplastin Time (aPTT) $\leq 1.5 \times$ ULN unless subject is receiving anticoagulant therapy as long as PT or PTT is within therapeutic range of intended use of anticoagulants
7. Women of childbearing potential (WOCBP) must have a negative serum pregnancy test within the 7 days prior to first dose of investigational product and a negative urine pregnancy test within the 3 days prior to first dose of investigational product, or a negative serum pregnancy test within the 3 days prior to first dose of investigational product
8. WOCBP must agree to follow instructions for method(s) of contraception for the duration of study treatment and 5 months after the last dose of investigational product. Males who are sexually active with WOCBP must agree to follow instructions for method(s) of contraception for the duration of study treatment and 7 months after the last dose of investigational product
9. Available archived or fresh tumor tissue sample for PD-L1 and other biomarker analysis
10. For subjects that consent to collection of tumor biopsies at study entry and before the first scheduled tumor assessment, primary or metastatic tumor that can be safely biopsied. A minimum of 24 subjects (6 subjects with each cohort/group) must consent to fresh core biopsies.

2.2.1.2 General Exclusion Criteria

1. Previous exposure to any immunomodulatory agents (e.g., anti- CD40, CTLA-4, PD-1/PD-L1, IDO inhibitors) with the following exceptions:
 - a. For Cohort 2 (unresectable or metastatic melanoma):
 - i. All subjects must have confirmed disease progression while on treatment with anti-PD-1/PD-L1 therapy
 - ii. Subjects could have received anti-CTLA-4 therapy provided they did not have disease progression while on therapy and they discontinue treatment with anti-CTLA-4 therapy at least 3 months prior to first dose of investigational product
 - b. For Cohort 3 (metastatic or locally advanced NSCLC):
 - i. All subjects must have disease progression while on treatment with anti-PD-1/PD-L1 therapy
2. Second malignancy (solid or hematologic) within the past 3 years except:
 - a. Adequately treated basal cell or squamous cell skin cancer, or
 - b. Carcinoma in situ of the cervix, or
 - c. Prostate cancer Gleason score < 6 with undetectable prostate specific antigen (PSA) over 12 months, or
 - d. Ductal breast carcinoma in situ with full surgical resection (i.e., negative margins), or
 - e. Treated medullary or papillary thyroid cancer
3. Active, known, clinically serious infections (\geq Grade 2 according to NCI-CTCAE v4.03) within the 14 days prior to first dose of investigational product
4. Use of systemic corticosteroids or other systemic immunosuppressive drugs within the 28 days prior to first dose of investigational product (except inhaled corticosteroids); the use of physiologic doses of corticosteroids may be approved after consultation with the

- Apexigen Medical Monitor (or designee)
5. Major surgery within 4 weeks of first dose of investigational product
 6. Concurrent treatment with any anti-cancer agent, except for hormonal therapy and palliative radiation as clinically indicated unless approved by the Medical Monitor
 7. History of allogeneic bone marrow transplantation
 8. Uncontrolled diabetes or hypertension
 9. Active autoimmune disease that has required systemic treatment in past 2 years (i.e. with use of disease modifying agents, corticosteroids or immunosuppressive drugs). Subjects with type I diabetes mellitus, hypothyroidism only requiring hormone replacement, skin disorders (such as vitiligo, psoriasis, or alopecia) not requiring systemic treatment, or conditions not expected to recur in the absence of an external trigger are permitted to enroll.
 10. History of (non-infectious) pneumonitis that required corticosteroids or current pneumonitis
 11. History of interstitial lung disease
 12. History of life-threatening toxicity related to prior anti-PD-1/PD-L1 treatment for subjects with metastatic melanoma except those that are unlikely to re-occur with standard countermeasures (e.g. hormone replacement after adrenal crisis)
 13. History of sensitivity or allergy to mAbs or IgG
 14. Congestive heart failure (New York Heart Association Class III to IV), symptomatic ischemia, conduction abnormalities uncontrolled by conventional intervention, or myocardial infarction within 6 months prior to the first dose of investigational product
 15. History of any thromboembolic event within 3 months prior to first dose of investigational product or an active coagulopathy
 16. Known active central nervous system (CNS) metastases and/or carcinomatous meningitis. Subjects with untreated brain metastases ≤ 3 mm that are asymptomatic, do not have significant edema, cause shift, require steroids or anti-seizure medications are eligible after discussion with the Medical Monitor. Lesions of any size in posterior fossa are excluded. Subjects with previously treated brain metastases may participate provided they are stable after treatment (without evidence of progression by imaging for at least 4 weeks prior to the first dose of trial treatment and any neurologic symptoms have returned to baseline), have no evidence of new or enlarging brain metastases, and are not using corticosteroids for at least 7 days prior to trial treatment. This exception does not include carcinomatous meningitis which is excluded regardless of clinical stability
 17. Known human immunodeficiency virus (HIV), hepatitis B or hepatitis C infection
 18. Has received a live-virus vaccination within 30 days of the first dose of investigational product. Seasonal flu vaccines that do not contain live virus are permitted
 19. Pregnant, breastfeeding, or unwilling to practice birth control during participation in the study
 20. Any clinically significant psychiatric, social, or medical condition that, in the opinion of the Investigator, could increase subject's risk, interfere with protocol adherence, or affect a subject's ability to give informed consent.

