3.1 Subject Enrollment and Treatment Administration

All subjects who sign a consent form will be assigned a unique Subject Identification Number. This number will be used to identify the subject throughout the study and must be used on all study documentation. Subjects will be considered enrolled after receiving any investigational product; consented subjects who do not receive investigational product will be considered screen failures.

The Apexigen Medical Monitor (or designee) will review the subject's information before enrollment. Only subjects who are approved by the Apexigen Medical Monitor (or designee) will be allowed to enroll in the study. During normal business days, a minimum of 24 hours will be required for the Apexigen Medical Monitor (or designee) to approve a subject for enrollment. Additional time may be required when approval is sought during a weekend or holiday.

Subject enrollment into a DL cohort of the Phase 1b dose-escalation or in the Phase 2 dose-expansion will follow the rules outlined in [Section 2.2](#).

On treatment days, nivolumab will be administered first, followed by APX005M.

During Phase 1b dose-escalation, in any of the multi-subject cohorts, the first two subjects must receive the first dose of investigational product at least 72 hours apart.

During the Phase 1b dose-escalation portion of the study all subjects will be monitored in the research clinic for 4 hours after the first 2 infusions of APX005M and as clinically indicated thereafter and during the Phase 2 dose-expansion portion of the study.

All subjects will be discharged from clinic after a clinical evaluation. Subjects should have stable vital signs including: lack of orthostatic hypotension (systolic blood pressure >100 mmHg, or no lower than 10 mm from baseline) without IV hydration (no hydration for at least 2 hours prior to discharge), lack of hypoxia (oxygen saturation >90% without oxygen), temperature <38°C, heart rate <110 beats/min.

After discharge, all subjects in Phase 1b should be monitored by a caregiver or by a healthcare professional for 24 hours after the first 2 infusions of APX005M and as clinically indicated thereafter. Subjects in the Phase 2 dose-expansion portion of the study should be monitored as clinically indicated.

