	4	Discontinue	Discontinue
Rash or other skin toxicity	2	Hold	Continue. Hold if > 7- 14 days
	3	Hold	Hold
	4	Discontinue	Discontinue
Neurological toxicity	2	Continue	Hold
	3-4	Hold	Discontinue
Hypotension, severe dehydration, shock out of proportion to current illness or suspected adrenal crisis	3	Hold. Dose reduction	Hold
	4	Discontinue	Discontinue
Fatigue	2 >6 weeks 3	Dose reduction	Grade 2: continue Grade 3: hold
Myocarditis	2	Hold	Hold
	3-4	Discontinue	Discontinue
All other drug-related non-hematologic toxicity	3 or Severe	1st occurrence: hold 2nd occurrence: dose reduction	Hold
	4	Discontinue [#]	Discontinue [#]
Hold = hold until retreatment criteria are met (Section 3.6) Dose reduction = reduce dose by one dose level in following cycle (Section 3.7) Discontinue = permanently discontinue that investigational product * Adrenal insufficiency requires discontinuation of nivolumab regardless of control with hormone replacement # Subjects may continue treatment for transient Grade 4 toxicity (such as electrolyte imbalances ≤ 72h, amylase or lipase increase) not associated with clinical sequelae after discussion with the Apexigen Medical Monitor (or designee).			

Dose reductions for APX005M are defined in [Table 5](#). Subjects requiring more than 2 dose reductions or a dose reduction below DL1, must discontinue APX005M.

Table 5: Modified DLs for APX005M Following Qualifying Suspected Adverse Reactions

Dose Level (mg/kg)	DL1 (0.03)	DL2 (0.1)	DL2a (0.2)	DL3 (0.3)
First Dose Reduction	Discontinue	0.06	0.1	0.2
Second Dose Reduction	Not applicable	0.03	0.06	0.1

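### Exclusion 12 bars prior life-threatening anti-PD-1/PD-L1 toxicity in melanoma only, although every Cohort 3 NSCLC subject is also pretreated and receives PD-1 blockade again

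*Protocol*

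**What the plan says.** Protocol 2.2.1.2, item 12, excludes "History of life-threatening toxicity related to prior anti-PD-1/PD-L1 treatment for subjects with metastatic melanoma" and then carves out a group, "except those that are unlikely to re-occur with standard countermeasures", with hormone replacement after adrenal crisis as the example. The Synopsis and SAP 2.3.2.3 carry the same melanoma-only limit.

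For Cohort 3, Protocol 2.2.1.1 states: "Subjects must have disease progression on an immediately preceding PD-1/PD-L1 containing regimen". It adds: "Subjects should start study treatment no later than 8 weeks following the last dose of anti-PD-1/PD-L1 containing regimen". Exclusion 1 has its own Cohort 3 branch, which again requires progression on anti-PD-1/PD-L1 treatment and says nothing about earlier toxicity. Cohort 3 then receives nivolumab 360 mg and APX005M every 21 days (Protocol 2.2).

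**The concern.** Two Phase 2 populations enter after anti-PD-1/PD-L1 therapy and are given PD-1 blockade again: melanoma (Cohort 2) and pretreated NSCLC (Cohort 3). Only the first is protected by an express bar on prior life-threatening toxicity from that drug class. The documents give no reason for the difference.

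The issue is patient safety. A Cohort 3 candidate who once had a life-threatening, recurrence-prone immune-related event, now resolved, can satisfy every written criterion. The Phase 1b data offer little reassurance on this history. Phase 1b took only immunotherapy-naïve NSCLC and melanoma, and item 12 applied to the melanoma subjects, so the RP2D was set with this history excluded by rule.

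**Working it through.** No formula underlies item 12. The check has three parts: whether another criterion closes the gap, whether the Cohort 3 entry rules explain it, and how many subjects it could touch.

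**Other provisions that reach Cohort 3**

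| Provision | What it catches | Bars a resolved Grade 4 colitis or hepatitis? |
|---|---|---|
| Inclusion 5: "Resolution of prior treatment-related toxicities to Grade 1, with the exception of alopecia" (and other listed exceptions) | Unresolved toxicity | No; a resolved event passes |
| Exclusion 4: "Use of systemic corticosteroids or other systemic immunosuppressive drugs within the 28 days prior to first dose of investigational product" | Recent steroid or immunosuppressant use | No; it is a washout, not a history rule |
| Exclusion 9 | Active autoimmune disease treated systemically in the past 2 years, with an exemption for externally triggered conditions | Not expressly |
| Exclusions 10 and 11 | Pneumonitis, interstitial lung disease | No |
| Exclusion 13 | Antibody or IgG allergy | No |
| Exclusion 14 | Listed cardiac conditions | No |
| Exclusion 20 | Conditions the investigator thinks raise risk | Discretionary |
| Protocol 3.1: "Only subjects who are approved by the Apexigen Medical Monitor (or designee) will be allowed to enroll in the study" | Anything the Medical Monitor declines | Discretionary |

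**Do the entry rules explain the difference?** Cohort 3 requires progression on the preceding regimen and a start within 8 weeks of its last dose. If the toxicity ended that regimen, the time available to finish steroids is at most

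8 × 7 = 56 days; 56 − 28 = 28 days.

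This narrows the gap, but an earlier event followed by resumed therapy is not limited in this way. Cohort 2 also has the 8-week limit and the requirement to progress on treatment, and still carries item 12. The entry rules therefore do not account for its absence in Cohort 3.

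**On-study comparison, by analogy only.** Protocol 3.7, Table 4, assigns Discontinue to both products for Grade 4 diarrhea/colitis, Grade 4 AST/ALT increase and Grade 3–4 myocarditis. The footnote reads: "Discontinue = permanently discontinue that investigational product". The table governs events during the study, not history, but it shows how the protocol regards such events.

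**Size.** Planned Cohort 3 numbers (Protocol 7.1):

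- Stage 1 only: 12 + 12 = 24.
- Both stages: 37 + 37 = 74. Phase 2 allows up to 156, so 74/156 ≈ 47%.

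These count response-evaluable subjects. Replacement of non-evaluable subjects, or enrolment into Stage 2 while Stage 1 is followed, would raise the number treated.

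The documents give no rate for the relevant history. Assume a proportion p of Cohort 3 subjects have it and pass all other criteria. The expected count is n·p, and the chance of at least one is 1 − (1 − p)^n.

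| p (assumed) | Expected, n = 24 | At least one, n = 24 | Expected, n = 74 | At least one, n = 74 |
|---|---|---|---|---|
| 0.5% | 0.12 | 11.3% | 0.37 | 31.0% |
| 1% | 0.24 | 21.4% | 0.74 | 52.5% |
| 3% | 0.72 | 51.9% | 2.22 | 89.5% |

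**The case against.** The strongest reply is that the gap is narrow and already largely covered.

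- **Judgment applies in both cohorts.** Item 12's exception needs a clinical view on recurrence, and exclusion 20 and Medical Monitor approval apply to everyone. Screening also records why prior immunotherapy was stopped (Protocol 5.2.1), so a regimen ended by a life-threatening event should come to light. This shows that many cases would probably be caught. It does not remove the difference: the same review applies to melanoma candidates, for whom the sponsor still wrote an express bar.
- **Exclusion 9 may cover it.** The Synopsis version is broader than the body and extends to known or suspected autoimmune disease. Whether checkpoint-inhibitor colitis or hepatitis falls under it is arguable, but neither version names such toxicity and both exempt conditions that need an external trigger.
- **The entry rules make such a subject rare.** This stands as a point about frequency. The 28 days is an upper limit, and an event after the last dose leaves less time.
- **The assumed range has no source in the documents.** This is true, and no count can be derived from them. The table shows only what would follow under that assumption.
- **Enrolment suspension.** The rule on Grade 3 or higher immune-related events (Protocol 2.2) is a further safeguard, but it acts only after harm has occurred.

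**Conclusion.** The concern holds. As written, a Cohort 3 subject with a resolved, recurrence-prone life-threatening toxicity from prior anti-PD-1/PD-L1 therapy meets every express criterion, while a melanoma subject with the same history does not. The reading of the text is firm. The number affected is unknown and probably small: about 0 to 2 subjects over the full cohort under the assumed 0.5% to 3%. The re-exposure is to PD-1 blockade rather than always to nivolumab, since the prior agent could be another drug; SAP 2.2.5 splits Cohort 3 by pembrolizumab and nivolumab. Alpha, power, sample size and analysis populations do not change. The correction should be made because the possible harm is serious and the change is cheap, but the validity of the trial does not depend on it.

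**What to change.** In item 12 of the Synopsis and Protocol 2.2.1.2, replace the restriction to metastatic melanoma with one covering subjects in Cohorts 2 and 3 and Phase 1b subjects with melanoma. Deleting the restriction altogether would have the same effect, because Cohort 1 is immunotherapy-naïve. Keep the existing exception, so that manageable histories such as a hormone-replaced endocrine event remain eligible. Make the same edit in SAP 2.3.2.3 for consistency only; the protective change is the one in the protocol.

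The cost is a few words in three places, IRB/IEC approval before implementation (Protocol 8.1.2) at the roughly 15 to 20 planned sites, and about 0 to 2 additional Cohort 3 screen failures under the assumed range. The change protects only subjects not yet enrolled; the SAP puts estimated last enrolment at Q2 2020.

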2.2.2 APX005M Dose

APX005M has been administered in the APX005M-001 study to subjects with solid tumors as a single-agent at 7 dose levels starting at 0.1 μ g/kg up to 1.0 mg/kg body weight every 21 days. At

0.6 and 1 mg/kg dose level 1 out of 6 subjects experienced a DLT. The RP2D for APX005M as a single agent every 21 days is 0.3 mg/kg body weight.

The proposed starting dose level for APX005M in this study is 0.03 mg/kg which is approximately 33 times lower than the highest dose of APX005M administered to human subjects. Three subjects were enrolled at this dose level in the APX005M-001 study and received a total of 8 infusions of APX005M. One additional subject enrolled at a lower dose level was allowed per protocol to have the dose of APX005M escalated and received 3 infusions of 0.03 mg/kg of APX005M. The only AE considered as possibly related to APX005M for all subjects receiving 0.03 mg/kg of APX005M was one event of vomiting (Grade 1) shortly after the administration of APX005M. This dose level was also the lowest to show a PDn effect across multiple markers of APC activation measured 24 hours after the start of infusion, although APX005M was detectable in the peripheral blood only during and at the end of infusion.

The highest dose level of APX005M to be tested in combination with nivolumab will be 0.3 mg/kg body weight (Table 1). At all dose levels proposed, APX005M has been well tolerated; all adverse reactions have been moderate (\leq Grade 2), transient and easily managed in outpatient setting. All available data suggests that 0.03 mg/kg every 21 days is a safe and pharmacodynamically active dose of APX005M.

